7.3.1 Primary endpoint analyses

Primary analyses

The statistical model used for the analysis of the primary endpoints will be an analysis of variance (ANOVA) model on the logarithmic scale. That is, the PK endpoints will be log-transformed (natural logarithm) prior to fitting the ANOVA model. This model will include effects accounting for the following sources of variation: sequence, subjects within

Proprietary confidential information © 2020 Boehringer Ingelheim International GmbH or one or more of its affiliated companies

sequences, period, treatment and metabolic state (fed or fasted) as well as the treatment-by-metabolic state interaction. The effect 'subjects within sequences' will be considered as random, whereas the other effects will be considered as fixed. The model is described by the following equation:

$$Y_{ijklm} = \mu + \zeta_i + s_{im} + \pi_j + \tau_k + \gamma_l + \varphi_{kl} + e_{ijklm}, \text{ where}$$

Y_{ijklm} = logarithm of response measured on subject m in sequence i receiving treatment k under metabolic state l in period j,

μ = the overall mean,

ζ_i = the i^{th} sequence effect, $i = 1, \dots, 10$

s_{im} = the effect associated with the m^{th} subject in the i^{th} sequence,
 $m = 1, 2, \dots, n_i$

π_j = the j^{th} period effect, $j = 1, \dots, 5$

τ_k = the k^{th} treatment effect, $k = 1, 2, 3$

γ_l = the l^{th} metabolic state, $l = 1$ (fed), 2 (fasted)

φ_{kl} = the k^{th} treatment effect ($k=1, 2, 3$) in the the l^{th} metabolic state ($l=1$ (fed), 2 (fasted))

e_{ijklm} = the random error associated with the m^{th} subject in sequence i who received treatment k for metabolic state l in period j.

where $s_{im} \sim N(0, \sigma_B^2)$ i.i.d., $e_{ijklm} \sim N(0, \sigma_W^2)$ i.i.d. and s_{im} , e_{ijklm} are independent random variables.

Point estimates for the ratios of the geometric means ($T_{\text{fed}}/R1_{\text{fed}}$, $T_{\text{fasted}}/R1_{\text{fasted}}$, and $T_{\text{fasted}}/R2_{\text{fasted}}$) for the primary endpoints (see Section 2.1) and their two-sided 90% confidence intervals (CIs) will be provided.

For each endpoint, the difference between the expected means for $\log(T_{\text{fed}})-\log(R1_{\text{fed}})$, $\log(T_{\text{fasted}})-\log(R1_{\text{fasted}})$ and $\log(T_{\text{fasted}})-\log(R2_{\text{fasted}})$ will be estimated by the difference in the corresponding adjusted means (Least Squares Means). Additionally their two-sided 90% confidence intervals will be calculated based on the residual error from the ANOVA and quantiles from the t-distribution. These quantities will then be back-transformed to the original scale to provide the point estimate and 90% CIs for each endpoint.

Bioequivalence is considered established if the 90% confidence intervals of the geometric means for the primary endpoints are contained in the pre-defined acceptance range, see Section 7.2.

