Statistical methods	
The assessment of bioequivalence will be based upon 2-sided 90% confidence intervals (CIs) for the ratios of the geometric means (test/reference) for the primary endpoints using an acceptance range of 80.00 to 125.00%. This method corresponds to the two one-sided t-tests procedure, each at a 5% significance level. The statistical model will be an analysis of variance (ANOVA) on the logarithmic scale including effects for sequence, subjects nested within sequences, period, treatment and metabolic state (fed or fasted) as well as the treatment-by-metabolic state interaction. CIs will be calculated based on the residual error from the ANOVA and quantiles from the t-distribution.
 
Descriptive statistics will be calculated for all endpoints.

Proprietary confidential information © 2020 Boehringer Ingelheim International GmbH or one or more of its affiliated companies

FLOW CHART

Period	Visit	Day	Planned time (relative to drug administration) [h:min]	Approximate clock time of actual day [h:min]	Event and comment	Safety laboratory ⁸	PK blood (Apremilast)	Vital signs (BP, PR)	Questioning for AEs and concomitant therapy ⁶
SCR	1	-23 to -1			Screening (SCR) ¹	A		x	
1/2/3/4/5 ⁷	2/3/4/5/6 ⁷	-1	-12:00	20:00	Admission to trial site	x ⁵			x
			-11:30	20:30	Snack (voluntary) ³				
		1	-1:00	07:00	Allocation to treatment ² (visit 2 only)	B ²	x ²	x ²	x ²
			-0:30	07:30	Start of high fat, high calorie breakfast prior to treatments T _{fed} and R1 _{fed}				
			0:00	08:00	Drug administration				
			0:30	08:30		x			
			1:00	09:00		x			
			1:30	09:30		x			
			2:00	10:00	240 mL fluid intake	x		x	
			2:30	10:30		x			
			3:00	11:00		x			
			3:30	11:30		x			
			4:00	12:00	240 mL fluid intake	x		x	
			5:00	13:00	Lunch ³	x			
			6:00	14:00		x			
			8:00	16:00		x			
			10:00	18:00	Dinner				
			11:00	19:00		x			
			15:00	23:00		x		x	
		2	24:00	08:00	Breakfast (voluntary) ³ , discharge from trial site	B	x	x	x
			36:00	20:00	Ambulatory visit		x		x
			48:00	08:00	Ambulatory visit		x		x
FU	7	5 to 11			End of trial (EoTrial) examination ⁴	C		x	x

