7.2 NULL AND ALTERNATIVE HYPOTHESES

Although there are multiple primary endpoints, an alpha adjustment is not needed because it is required that all primary endpoints meet the equivalence criterion as described below simultaneously. Therefore, a one-sided alpha of 5% will be used for testing.

The assessment of bioequivalence of 30 mg of EU-sourced Otezla® compared with 30 mg of US-sourced Otezla® under fed conditions (T_{fed} versus $R1_{\text{fed}}$) and 30 mg of EU-sourced Otezla® compared with 30 mg of US-sourced Otezla® and 30 mg of Japan-sourced Otezla® under fasted conditions (T_{fasted} versus $R1_{\text{fasted}}$ versus $R2_{\text{fasted}}$) will be based upon two-sided 90% confidence intervals (CIs) for the ratio of the geometric means ($T_{\text{fed}}/R1_{\text{fed}}$, $T_{\text{fasted}}/R1_{\text{fasted}}$, and $T_{\text{fasted}}/R2_{\text{fasted}}$, respectively) for the primary endpoints using an acceptance range of 80.00 to 125.00%. This method is equivalent to the two-sided t-test procedure, each at the 5% significance level.

The following hypotheses are tested:

Null hypothesis H_0 (Inequivalence): $\mu_T - \mu_R \leq -\delta$ or $\mu_T - \mu_R \geq \delta$

where μ_T and μ_R are the means of the log-transformed endpoint for the test and reference treatments, respectively, and δ is the bioequivalence limit that defines the acceptance range on the logarithmic scale.

Alternative hypothesis H_a (Equivalence): $-\delta < \mu_T - \mu_R < \delta$,

with T referring to the test treatment in fasted or fed state and R to the reference treatment in fasted or fed state.

Proprietary confidential information © 2020 Boehringer Ingelheim International GmbH or one or more of its affiliated companies

In this trial, the bioequivalence limit δ is $\ln(1.25)$. By back-transforming (exponentiating), this translates to an acceptance range of 80.00 to 125.00% for the ratio of the geometric means ($T_{\text{fed}}/R1_{\text{fed}}$ or $T_{\text{fasted}}/R1_{\text{fasted}}$, $T_{\text{fasted}}/R2_{\text{fasted}}$, respectively) for endpoints on the original scale.

The rejection of the null hypothesis at the $\alpha = 0.05$ level is equivalent to the inclusion of the 90% confidence interval for $\mu_T - \mu_R$ in the acceptance range $(-\delta, \delta)$.

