7.7 DETERMINATION OF SAMPLE SIZE

The sample size for this trial was determined using assumptions on the intra-individual variability of the primary endpoints based on the relative bioavailability trial CC-10004-CP-022 and food-effect trial CC-10004-BA-002 both reported by the European Medicines Agency in the Assessment Report for Otezla® [R18-1250]. For C_{max} the geometric coefficient of variation (gCV) was estimated to be about 23% in CC-10004-CP-022 and about 28% in CC-10004-BA-002, while for AUC_{0-tz} the gCV was about 8% and 20%, respectively.

A sample size of 40 subjects is needed to achieve 90% power to reject both one-sided null hypotheses for C_{max} each at the 5% level of significance in favor of bioequivalence.

Due to the high correlation between the primary endpoints, only C_{max} will be considered for power calculations. Using a sample size of 40 subjects (4 per sequence group), the power to reject both one-sided null hypotheses for one parameter each at the 5% level of significance in favour of bioequivalence is displayed in Table 7.7: 1, under various assumptions for the T/R ratio. To account for the uncertainty of the assumed gCV, a range of gCVs around 26% is also presented.

Table 7.7: 1

Power for concluding bioequivalence (acceptance range 80-125%) based on a geometric coefficient of variation around 26% and for different expected ratios of geometric means (T/R) in a five-period, ten-sequence crossover trial (N=40, 4 per sequence)

gCV[%]	Ratio[%]*						
	92.5	95	97.5	100	102.5	105	107.5
20	94.7	98.7	99.7	>99.9	99.8	98.9	96.0
26	81.1	91.0	96.0	97.5	96.1	91.7	83.6
28	76.0	87.0	93.2	95.1	93.3	87.8	78.7

* Ratio of geometric means (T/R) for a PK endpoint is defined by $\exp(\mu_T)/\exp(\mu_R)$.

From the above table, a sample size of 40 will yield approximately 90% power to conclude bioequivalence for an assumed gCV of 26%, if the ratio is not more than 5% different from the ratio of 100%, which reflects no difference in exposure. In addition, this sample size still provides more than 80% power, if the ratio is not more than 7.5% different from 100% under the assumption of a gCV of 26% in both cases.

The calculations were performed as described in 'Using SAS Proc Power to perform model-based power analysis for clinical pharmacology studies [R20-3405] using SAS version 9.4.

8. INFORMED CONSENT, TRIAL RECORDS, DATA PROTECTION, PUBLICATION POLICY, AND ADMINISTRATIVE STRUCTURE

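### Should each bioequivalence interval take its residual variance from its own metabolic state rather than from one residual pooled over fasted and fed periods?

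*Protocol*

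**What the plan says.** Protocol 7.3.1 models the log-transformed endpoints with sequence, subject within sequence, period, treatment, metabolic state and the treatment-by-state interaction. Subjects are random, and the errors are independent with one common variance. Three ratios are wanted: T/R1 fed, T/R1 fasted and T/R2 fasted. For these, "two-sided 90% confidence intervals will be calculated based on the residual error from the ANOVA and quantiles from the t-distribution". The synopsis agrees: "CIs will be calculated based on the residual error from the ANOVA".

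Protocol 7.2 makes the intervals the decision rule, "using an acceptance range of 80.00 to 125.00"%, and states that "a one-sided alpha of 5% will be used for testing".

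Protocol 7.7 takes its variability from two earlier trials. For Cmax the gCV was about 23% in the relative bioavailability trial and about 28% in the food-effect trial. For AUC0-tz "the gCV was about 8% and 20%, respectively". The trial is powered on one value for Cmax, with "approximately 90% power to conclude bioequivalence for an assumed gCV of 26%, if the ratio is not more than 5% different" from 100%.

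SAP Section 4 reports termination with 20 of the 40 planned subjects and limits PK parameters to descriptive statistics. SAP 7.4 states that the evaluation in protocol 7.3.1 is not carried out.

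**The concern.** All three contrasts lie within one metabolic state, yet the variance behind each interval is pooled over both. Three of the five periods are fasted, so the fed interval rests mostly on fasted data. A common variance is an assumption, and the protocol neither justifies it nor plans a sensitivity analysis.

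The planning figures invite doubt: the higher gCVs come from the food-effect trial, and for AUC0-tz they differ by a factor of 2.5. If fed dosing were the more variable, the fed interval would be too narrow and could declare bioequivalence falsely more than 5% of the time, while the fasted intervals would be too wide. The waiver of alpha adjustment in 7.2 requires each component test to hold its level. Separate models by state look like an inexpensive remedy.

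**Working it through.** **Inputs.** N = 40, 4 per sequence, and the ten sequences of Table 3.1: 1 (protocol 3.1, 7.7); limits ±ln(1.25) and one-sided 5% (7.2); gCVs of 23% and 28% for Cmax, 8% and 20% for AUC0-tz (7.7).

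**Formulas.** σ² = ln(1 + gCV²). The standard error of a log ratio is √(2σ²/40). The half-width is t(0.95, df) times the estimated standard error. Power is the probability that the whole interval lies inside the limits, integrated over the distribution of the residual variance.

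**Degrees of freedom.**
- Pooled: 200 observations − 40 subjects − 4 periods − 4 treatment-state terms = 152.
- Fasted only: 120 − 40 − 4 − 2 = 74.
- Fed only: 80 − 40 − 4 − 1 = 35.

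**The plan's own figure.** At gCV 26%, σ² = ln(1.0676) = 0.0654 and the standard error is √(2 × 0.0654/40) = 0.0572. With 152 df, power at a ratio of 95% is 91.0%, as in Table 7.7: 1. All 21 cells agree within 0.1 point. Paired analysis with 39 df would give 90.3%, so the table does assume the pooled residual.

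**Effect of unequal variances.** The pooled variance is 0.6σ²(fasted) + 0.4σ²(fed). For Cmax at 23% fasted and 28% fed it is 0.6 × 0.0515 + 0.4 × 0.0755 = 0.0611, a gCV of 25.1%. The width relative to the correct one is √(0.0611/0.0755) = 0.90 fed and √(0.0611/0.0515) = 1.09 fasted. Error rates below come from at least 20,000 simulated trials per case with a true ratio of 0.80 (simulation error about 0.2 to 0.4 points). Assigning the trial gCVs to states is an assumption, so both directions are shown.

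| Assumed gCV, fasted / fed | Pooled gCV | Relative width, fed | Relative width, fasted | Error, fed | Error, fasted |
|---|---|---|---|---|---|
| 26% / 26% | 26% | 1.00 | 1.00 | about 5% | about 5% |
| Cmax 23% / 28% | 25.1% | 0.90 | 1.09 | about 7% | about 3.7% |
| Cmax 28% / 23% | 26.1% | 1.13 | 0.93 | about 3% | about 6% |
| AUC0-tz 8% / 20% | 14.0% | 0.71 | 1.75 | about 12% | about 0.3% |
| AUC0-tz 20% / 8% | 16.3% | 2.02 | 0.82 | 0.1% or less | about 9% |

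**Subject-by-food interaction instead.** With an assumed interaction SD of 0.15 and 26% in both states, the interaction inflates the pooled residual but cancels in every within-state contrast. All three intervals are then slightly wide, with errors of about 4 to 4.5%.

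**Separate fits by state.** With complete data the variance multiplier stays at 2/40; only the residual and its df change. Error returns to about 5% in every case above. At equal 26%, power at a ratio of 95% goes from 91.0% to 90.8% (fasted, 74 df) and 90.2% (fed, 35 df). At Cmax 23%/28%, fed power is about 86%, against about 90% from the pooled fit, whose interval is then too narrow.

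**What the current plan computes.** SAP Section 7 lists the PK parameter statistics: mean, SD, median, range, CV, geometric mean, geometric CV and percentiles, each from individual values. None uses the ANOVA residual.

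**The case for a change.** The strongest case for a change is that protocol 7.3.1 is the only written inferential analysis. Its decision rule rests on an equal-variance assumption that the planning data do not support, and an unequal split in either direction breaks one of the tests. The remedy keeps the same contrasts and is almost free if the variances are equal. SAP 6.3 also still reproduces protocol wording about model-based and inferential statistics, so someone might yet run the model on the 20 subjects.

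Part of this stands. The assumption is unjustified, and separate fits would be the safer specification.

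The rest is weaker. Each gCV in 7.7 belongs to a whole trial, and a food-effect trial normally mixes both states, so neither a fed/fasted difference nor its direction is shown. The 12% figure is for one endpoint at exactly the limit, whereas 7.2 requires all primary endpoints to pass, so the joint error cannot exceed it. The wording in SAP 6.3 is quoted from the protocol, and SAP Sections 4 and 7.4 expressly withdraw the evaluation.

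**Conclusion.** No change is needed. The protocol does pool one residual variance over both states, and if the source-trial gCVs were state-specific the per-endpoint error in the more variable state would be about 6 to 7% for Cmax and about 9 to 12% for AUC0-tz. That condition is an assumption which the documents neither support nor exclude; a subject-by-food interaction would instead make all three intervals conservative.

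The deciding fact is that the final SAP cancels the analysis. No bioequivalence decision is taken and the SAP text plans no interval or ratio for the 20 treated subjects, so revising the variance model would gain nothing in this trial's report. This rests on SAP Sections 4 and 7.4 being followed as written. If the 7.3.1 analysis were run after all, or the design used again, the variance assumption should be reconsidered, recognising that at Cmax 23%/28% the true fed power is about 86% rather than 90%.

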7.3.2 Secondary endpoint analyses

Not applicable.

7.3.4 Safety analyses

Safety will be analysed based on the assessments described in Section [2.2.2.2](#). All treated subjects (TS, refer to Section [7.2](#)) will be included in the safety analysis. Safety analyses will be descriptive in nature and based on BI standards. No hypothesis testing is planned.

For all analyses, the treatment actually administered (= treatment at onset) to the subject will be used (any deviations from the randomised treatment will be discussed in the minutes of the Report Planning Meeting).

Treatments will be compared in a descriptive way. Tabulations of frequencies/proportions will be used to evaluate categorical (qualitative) data, and tabulations of descriptive statistics will be used to analyse continuous (quantitative) data.

Measurements (such as ECG, vital signs, or laboratory parameters) or AEs will be assigned to treatments (see Section [4.1](#)) based on the actual treatment at the planned time of the measurement or on the recorded time of AE onset (concept of treatment emergent AEs). Therefore, measurements planned or AEs recorded prior to first intake of trial medication will be assigned to the screening period, those between first trial medication intake and end of REP (see Section [1.2.2](#)) will be assigned to the treatment period. Events occurring after the REP but prior to next intake or end of trial termination date will be assigned to 'follow-up'. In case of two or more treatments, the follow-up will be summarized according to the previous treatment. These assignments including the corresponding time intervals will be defined in detail in the TSAP. Note that AEs occurring after the last per protocol contact but entered before final database lock will be reported to Pharmacovigilance only and will not be captured in the trial database.

Additionally, further treatment intervals (analysing treatments) may be defined in the TSAP in order to provide summary statistics for time intervals, such as combined treatments, on-treatment totals, or periods without treatment effects (such as screening and follow-up intervals).

Proprietary confidential information © 2020 Boehringer Ingelheim International GmbH or one or more of its affiliated companies

Adverse events will be coded using the Medical Dictionary for Regulatory Activities (MedDRA). Frequency, severity, and causal relationship of AEs will be tabulated by treatment, system organ class, and preferred term. SAEs, AESIs (see Section [5.2.6.1](#)), and other significant AEs (according to ICH E3) will be listed separately.

Previous and concomitant therapies will be presented per treatment group without consideration of time intervals and treatment periods.

Laboratory data will be compared to their reference ranges. Values outside the reference range as well as values defined as possibly clinically significant will be highlighted in the listings. Additionally, differences from baseline will be evaluated.

Vital signs or other safety-relevant data will be assessed with regard to possible on-treatment changes from baseline.

Relevant ECG findings will be reported as AEs.

The TSAP will provide further details.

7.4 INTERIM ANALYSES

No interim analysis is planned.

7.5 HANDLING OF MISSING DATA

7.5.1 Safety

It is not planned to impute missing values for safety parameters.

7.5.2 Pharmacokinetics

Handling of missing PK data will be performed according to the relevant Corporate Procedure ([001-MCS-36-472](#)).

PK parameters that cannot be reasonably calculated based on the available drug concentration-time data will not be imputed.

7.6 RANDOMISATION

Subjects will be randomised to one of the 10 treatment sequences in equal numbers. The block size will be documented in the CTR.

The sponsor will arrange for the randomisation as well as packaging and labelling of trial medication. The randomisation list will be generated using a validated system that uses a pseudo-random number generator and a supplied seed number so that the resulting allocation is both reproducible and non-predictable.

The randomisation list will contain additional blocks to allow for subject replacement (refer to Section [3.3.5](#)).

7.7 DETERMINATION OF SAMPLE SIZE

The sample size for this trial was determined using assumptions on the intra-individual variability of the primary endpoints based on the relative bioavailability trial CC-10004-CP-022 and food-effect trial CC-10004-BA-002 both reported by the European Medicines Agency in the Assessment Report for Otezla® [R18-1250]. For C_{max} the geometric coefficient of variation (gCV) was estimated to be about 23% in CC-10004-CP-022 and about 28% in CC-10004-BA-002, while for AUC_{0-tz} the gCV was about 8% and 20%, respectively.

A sample size of 40 subjects is needed to achieve 90% power to reject both one-sided null hypotheses for C_{max} each at the 5% level of significance in favor of bioequivalence.

Due to the high correlation between the primary endpoints, only C_{max} will be considered for power calculations. Using a sample size of 40 subjects (4 per sequence group), the power to reject both one-sided null hypotheses for one parameter each at the 5% level of significance in favour of bioequivalence is displayed in Table 7.7: 1, under various assumptions for the T/R ratio. To account for the uncertainty of the assumed gCV, a range of gCVs around 26% is also presented.

Table 7.7: 1

Power for concluding bioequivalence (acceptance range 80-125%) based on a geometric coefficient of variation around 26% and for different expected ratios of geometric means (T/R) in a five-period, ten-sequence crossover trial (N=40, 4 per sequence)

gCV[%]	Ratio[%]*						
	92.5	95	97.5	100	102.5	105	107.5
20	94.7	98.7	99.7	>99.9	99.8	98.9	96.0
26	81.1	91.0	96.0	97.5	96.1	91.7	83.6
28	76.0	87.0	93.2	95.1	93.3	87.8	78.7

* Ratio of geometric means (T/R) for a PK endpoint is defined by $\exp(\mu_T)/\exp(\mu_R)$.

From the above table, a sample size of 40 will yield approximately 90% power to conclude bioequivalence for an assumed gCV of 26%, if the ratio is not more than 5% different from the ratio of 100%, which reflects no difference in exposure. In addition, this sample size still provides more than 80% power, if the ratio is not more than 7.5% different from 100% under the assumption of a gCV of 26% in both cases.

The calculations were performed as described in 'Using SAS Proc Power to perform model-based power analysis for clinical pharmacology studies [R20-3405] using SAS version 9.4.

8. INFORMED CONSENT, TRIAL RECORDS, DATA PROTECTION, PUBLICATION POLICY, AND ADMINISTRATIVE STRUCTURE

The trial will be carried out in compliance with the protocol, the ethical principles laid down in the Declaration of Helsinki, in accordance with the ICH Harmonized Guideline for Good Clinical Practice (GCP), relevant BI Standard Operating Procedures (SOPs), the EU regulation 536/2014, and other relevant regulations. Investigators and site staff must adhere to these principles.

Standard medical care (prophylactic, diagnostic, and therapeutic procedures) remains the responsibility of the subject's treating physician.

The investigator will inform the sponsor immediately of any urgent safety measures taken to protect the trial subjects against any immediate hazard, as well as of any serious breaches of the protocol or of ICH GCP.

The Boehringer Ingelheim transparency and publication policy can be found on the following web page: trials.boehringer-ingelheim.com. As a general rule, no trial results should be published prior to archiving of the CTR.

The terms and conditions of the insurance coverage are made available to the investigator and the subjects, and are stored in the ISF.

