1. INTRODUCTION

1.1 MEDICAL BACKGROUND

BI 730357 is being developed for the treatment of patients with moderate to severe plaque psoriasis and is also under development for the treatment of other disease indications such as psoriatic arthritis, ankylosing spondylitis, and inflammatory bowel disease.

Boehringer Ingelheim (BI) intends to conduct two parallel pivotal Phase III trials designed to demonstrate the superiority of BI 730357 to apremilast (trade name Otezla[®]) as active comparator.

BI currently assumes that each pivotal trial will be conducted globally and plans to use apremilast (Otezla[®]) sourced from three ICH regions (EU, US, and Japan) as the active comparator in the planned Phase III studies of BI 730357.

Apremilast, an inhibitor of phosphodiesterase 4 (PDE4), has been approved in the US since 2014 for the treatment of patients with active psoriatic arthritis, and since 2015 for the treatment of moderate to severe plaque psoriasis. In the EU, apremilast is approved in both indications, psoriasis and psoriatic arthritis. In Japan, apremilast is approved since 2017 for the treatment of plaque psoriasis with inadequate response to topical treatment, and the treatment of psoriatic arthritis. In all three ICH regions, the recommended maintenance dose of apremilast is 30 mg twice daily taken orally (following initial titration starting with 10 mg once daily) [[R20-3168](#), [R20-3173](#), [R20-3422](#)].

Proprietary confidential information © 2020 Boehringer Ingelheim International GmbH or one or more of its affiliated companies

BI intends to use either EU-sourced Otezla® only or EU-sourced Otezla® and US-sourced Otezla® as active comparator in the planned Phase III studies for marketing authorization.

BI conducts this bioequivalence study for the 30 mg strength to demonstrate bioequivalence between EU-approved Otezla®, US-licensed Otezla® and Japan-approved Otezla® tablet formulations in order to allow bridging of the Japan-, US- and EU-sourced Otezla® drug products, i.e. the usage of either EU-approved Otezla® only, or EU-approved and US-licensed Otezla®/Japan-approved Otezla®, in the planned Phase III trials for marketing authorization.

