2. TRIAL OBJECTIVES AND ENDPOINTS

2.1 MAIN OBJECTIVES, PRIMARY AND SECONDARY ENDPOINTS

2.1.1 Main objectives

The main objective of this trial is to demonstrate bioequivalence (BE) between EU-sourced Otezla® film-coated tablets (Test, T), US-sourced Otezla® film-coated tablets (Reference 1, R1) and Japan-sourced Otezla® film-coated tablets (Reference 2, R2) in the strength of 30 mg. All tablet formulations will be tested for bioequivalence in the fasted state (BE under fasting conditions, i.e. T_{fasted} versus $R1_{\text{fasted}}$ and T_{fasted} versus $R2_{\text{fasted}}$) as well as for the EU- and US-formulation in the fed state (BE under fed conditions, i.e. T_{fed} versus $R1_{\text{fed}}$).

[figure not shown]

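### Should the roughly 90% power in Protocol section 7.7 be restated because the trial has three bioequivalence comparisons?

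*Protocol*

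**What the plan says.** Protocol section 7.7 sizes the trial on Cmax alone. It says: "A sample size of 40 subjects is needed to achieve 90% power to reject both one-sided null hypotheses" for that endpoint. It introduces Table 7.7: 1 as "the power to reject both one-sided null hypotheses for one parameter each at the 5% level of significance", and the table's footnote defines a single ratio of one test mean to one reference mean. The table title begins "Power for concluding bioequivalence (acceptance range 80-125" and goes on to state N=40 with 4 per sequence. Two summary statements follow. The first is "From the above table, a sample size of 40 will yield approximately 90% power to conclude bioequivalence for an assumed gCV of 26" per cent, for a ratio within 5% of unity. The second is "this sample size still provides more than 80% power, if the ratio is not more than 7.5% different from 100" per cent, again at gCV 26%.

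Section 2.1.1 begins "The main objective of this trial is to demonstrate bioequivalence (BE) between EU-sourced Otezla® film-coated tablets (Test, T" and goes on to list three comparisons: T against R1 fasted, T against R2 fasted, and T against R1 fed. Section 7.2 justifies an unadjusted 5% level by requiring all primary endpoints to meet the criterion together, and section 7.3.1 words its success rule in terms of primary endpoints. Neither says whether the three comparisons stand or fall together.

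**The concern.** One main objective with three comparisons invites the reading that the trial succeeds only if all three pass. Section 7.7 gives the only power figures in the plan, and neither its table title nor its two summary statements mention comparisons. A reader could take about 90% as the chance that the whole objective is met.

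Under an all-three rule that would be too optimistic. At gCV 26% both summary statements would fail at the edge of their own ranges: 77-79% instead of about 90% when the ratios are 5% off, and 57-62% instead of more than 80% when they are 7.5% off. A sponsor wanting 90% joint power at 0.95 and 1.05 would have found 40 subjects too few. Fifty subjects give 88.1% and 89.2%, and sixty give 94.1% and 94.7%.

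**Working it through.** **Inputs.** From the protocol: N=40, 4 per sequence (7.7); one-sided alpha 5% and limits ±ln 1.25 = ±0.2231 (7.2); gCV 26% for Cmax (7.7); five treatments per subject in ten sequences (3.1); one pooled residual error with t quantiles (7.3.1).

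**One comparison, the plan's own figure.**

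- Log-scale SD: √ln(1 + 0.26²) = 0.2558.
- Standard error of a contrast: 0.2558 × √(2/40) = 0.0572.
- Residual df: 200 − 1 − 39 − 4 − 4 = 152, so the t quantile is 1.655.
- Ratio 1.00: 0.2231/0.0572 − 1.655 ≈ 2.25 on each side, and 2Φ(2.25) − 1 ≈ 97.5%.
- Ratio 0.95 (ln = −0.0513): the nearer limit gives (0.2231 − 0.0513)/0.0572 − 1.655 ≈ 1.35, and Φ(1.35) ≈ 91%. The farther limit costs less than 0.1 point.

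Integrating over the distribution of the residual variance gives the gCV 26% row exactly: 81.1 / 91.0 / 96.0 / 97.5 / 96.1 / 91.7 / 83.6% for ratios 0.925 to 1.075. All 21 cells of Table 7.7: 1 reproduce to within 0.05 points. The smallest N with 90% power for one comparison at 0.95 is 39 (38 gives 89.7%, 39 gives 90.4%). The next multiple of ten sequences is 40, so the planned N matches sizing for a single comparison.

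**Comparisons taken together.** Least squares on the ten sequences of Table 3.1: 1 with 4 subjects each gives contrast variances of 0.05 in units of the residual variance. The covariance between the two fasted contrasts, which share T fasted, is 0.025 (correlation 0.5). The fed contrast has covariance 0 with both. With a common true ratio, gCV 26% and 40 completers:

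| True ratio | One comparison | EU/US fasted and fed | All three |
|---|---|---|---|
| 0.925 | 81.1% | 65.8% | 57.1% |
| 0.95 | 91.0% | 82.9% | 77.2% |
| 0.975 | 96.0% | 92.2% | 89.2% |
| 1.00 | 97.5% | 95.0% | 92.9% |
| 1.025 | 96.1% | 92.4% | 89.4% |
| 1.05 | 91.7% | 84.1% | 78.7% |
| 1.075 | 83.6% | 70.0% | 61.8% |

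At gCV 28% the all-three figures are 68.5% at 0.95, 86.7% at 1.00 and 70.2% at 1.05.

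**Which column does section 7.7 claim?** The sizing sentence and the sentence introducing the table both refer to rejecting two one-sided null hypotheses. Section 7.2 writes that pair for one test mean and one reference mean, so two nulls are one comparison; three comparisons would have six. The footnote defines one ratio. The first summary statement is drawn expressly from the table, and both speak of a single ratio, so they carry the table's scope. The claim is the one-comparison column, and that column is right.

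**Does the plan require all three to pass?** No passage says so. The requirement in section 7.2 and the success rule in section 7.3.1 concern endpoints. Section 1.1 gives the aim "in order to allow bridging of the Japan-, US- and EU-sourced Otezla® drug products", which leaves a joint reading open, but it also says: "BI intends to use either EU-sourced Otezla® only or EU-sourced Otezla® and US-sourced Otezla® as active comparator". That use does not need the Japanese comparison, and neither does the rationale in section 1.3.

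**The case for a change.** The best case for a change is that the limit to one endpoint is explicit but the limit to one comparison is only implied. Section 7.7 gives a reason for leaving out the AUC endpoints (high correlation with Cmax) and none for leaving out two comparisons. Nor does the point rest on the Japanese product. Section 1.3 says the EU and US tablets are to be studied fed as well as fasted, and if both of those must pass, power is 83-84% at 5% off and 66-70% at 7.5% off. A label would cost almost nothing.

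The numbers stand, and so does the observation that the title and the two summary statements do not repeat the qualifier. The step from there to a misstated power does not stand. Each lower figure is the power of a compound claim that the plan never defines, whereas the stated figures are the power of the test that section 7.7 describes. If the claims are separate, the stated figures are correct for each and a joint figure answers a question nobody asked. If the claims are joint, the lower figures apply, but requiring every comparison to pass needs no alpha adjustment, and the model and the 90% confidence intervals are unchanged.

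**Conclusion.** No change follows. Table 7.7: 1 and its two summary statements are correct for one test/reference comparison on Cmax with 40 completers, and the surrounding wording lets a statistician read them that way. What is left is a qualifier not repeated and a joint-or-separate rule not written down. A reader can fill the first from the text, and each of the three intervals supports its own conclusion whichever way the second is settled.

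The gap between the readings is real but conditional. At gCV 26% it is 97.5% against 92.9% at a ratio of 1.00, and 91.0% against 77.2% at 0.95. This assumes an all-three rule, the same true ratio in each comparison, equal residual variance fed and fasted, 40 completers and Cmax alone. Nothing in the reported results depends on it: SAP section 4 records that the trial ended with 20 of 40 planned subjects, and SAP section 7.4 limits the primary endpoints to descriptive statistics.
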